##### **5.1.2 Target Volumes**

CT images will be segmented by the attending radiation oncologist to define the target volumes detailed below:

**GTVp:** The initial GTVp is defined as the pre-operative extent of all known gross primary disease determined from clinical information, endoscopic examination, MRI and PET images.

**GTVn:** The GTVn is defined as the pre-operative extent of all known pathologically-involved lymph nodes as determined from clinical information, CT, MRI, PET images and pathology reports.

**CTV\_High:** The high-dose CTV will be the entire post-operative bed including dissected lymph node levels regardless of whether there is pathologic evidence of lymph nodes.

**CTV\_Low:** The low-dose CTV will include any elective treatment areas including areas at risk near the primary site including at least a 1 cm anatomically-confined margin around the operative bed (i.e. the contralateral tongue or adjacent floor of mouth) and/or undissected lymph node beds at risk for disease involvement based upon the guidelines outlined in Biau et al. (Biau Green Journal 2019).

**Planning Target Volumes:** A margin no larger than 3 mm will be added to the CTV\_High and CTV\_Low to define the PTV\_High and PTV\_Low, respectively for daily changes in setup motion.

### 5.1.3 Critical Normal Tissues

Required critical normal tissues to be segmented (recommended labeling in *italics*) include unless those tissues were resected at the time of surgery (i.e. the Supraglottic and glottic larynx in a total laryngectomy patient):

- Brainstem (Brainstem)
- Spinal Cord (SpinalCord)
- Brainstem PRV 5 mm (Brainstem\_PRV03)
- Spinal Cord PRV 5 mm (SpinalCord\_PRV05)
- Left (OpticNrv\_L) and right (OpticNrv\_R) optic nerves
- Optic chiasm (OpticChiasm)
- Mandible (Bone\_Mandible)
- Left (Parotid\_L) and right (Parotid\_R) parotid glands
- Left (GlnD\_Submand\_L) and right (GlnD\_Submand\_R) submandibular glands
- Oral cavity (Oral\_Cavity)
- Lips (Lips)
- Supraglottic and glottic larynx (LarynxGSL)
- Pharyngeal constrictors (Pharynx)
- Trachea (Trachea)
- Esophagus on Slices with the PTV (Esophagus\_S)
- Left (BrachialPlexus\_L) and right (BrachialPlexus\_R) brachial plexus
- Patient (External)

### 5.1.4 Radiation Treatment Planning

The treatment plan will be based on the analysis of the volumetric dose, including dose volume histogram analyses of the PTVs and critical normal tissues. IMRT planning is mandatory.

#### 5.1.4.1 Dose Fractionation

Once daily radiation will be delivered as per the enrolled dose level of the patient:

	Target	Dose Level 1	Dose Level 2	Dose Level 3
D PTV_High	PTV_High	42 Gy in 10 fx	39 Gy in 8 fx	32.5 Gy in 5 fx
D PTV_Low	PTV_Low	38 Gy in 10 fx	34 Gy in 8 fx	29 Gy in 5 fx

#### 5.1.4.2 Dose Specification

The prescribed dose for each PTV volume should cover at least 95% of the volume. Additionally, 98% of the prescribed dose for each PTV volume should cover at least 98% of the volume.

As an acceptable deviation, 95% of the prescribed dose for each PTV volume should cover at least 95% of the volume. Additionally, 93% of the prescribed dose for each PTV volume should cover at least 98% of the volume.

### 5.1.4.3 Dose Constraints

#### Required

Structure	Dosimetric Parameter	Per Protocol	Variation Acceptable
PTV_High	D 95% D 98%	D PTV_High 98% of D PTV_High	95% of D PTV_High 93% of D PTV_High
PTV_Low	D 95% D 98%	D PTV_Low 98% of D PTV_Low	95% of D PTV_Low 93% of D PTV_Low
Patient	D 0.03cc	106% D PTV_High	110% D PTV_High

#### Dose Level 1 (42 Gy in 10 fractions)

Structure	Dosimetric Parameter	Per Protocol	Variation Acceptable
Spinal Cord	D 0.03cc	20 Gy	30 Gy
Brainstem	D 0.03cc	20 Gy	30 Gy
SpinalCord_PRV05	D 0.03cc	20 Gy	30 Gy
Brainstem_PRV03	D 0.03cc	20 Gy	30 Gy
OpticNrv_L or OpticNrv_R	D 0.03cc	20 Gy	30 Gy
OpticChiasm	D 0.03cc	20 Gy	30 Gy
Mandible	D 0.03cc	30 Gy	108% D PTV_High
Esophagus	D 0.03cc	30 Gy	108% D PTV_High
Trachea	D 0.03cc	30 Gy	108% D PTV_High
BrachialPlexus_L or BrachialPlexus_R	D 0.03cc	30 Gy	105% D PTV_High

#### Dose Level 2 (39 Gy in 8 fractions)

Structure	Dosimetric Parameter	Per Protocol	Variation Acceptable
Spinal Cord	D 0.03cc	17.5 Gy	24 Gy
Brainstem	D 0.03cc	17.5 Gy	24 Gy
SpinalCord_PRV05	D 0.03cc	17.5 Gy	24 Gy
Brainstem_PRV03	D 0.03cc	17.5 Gy	24 Gy
OpticNrv_L or OpticNrv_R	D 0.03cc	17.5 Gy	24 Gy
OpticChiasm	D 0.03cc	17.5 Gy	24 Gy
Mandible	D 0.03cc	24 Gy	108% D PTV_High
Esophagus	D 0.03cc	24 Gy	108% D PTV_High
Trachea	D 0.03cc	24 Gy	108% D PTV_High
BrachialPlexus_L or BrachialPlexus_R	D 0.03cc	24 Gy	105% D PTV_High

*Dose Level 3 (32.5 Gy in 5 fractions)*

Structure	Dosimetric Parameter	Per Protocol	Variation Acceptable
Spinal Cord	D 0.03cc	15 Gy	20 Gy
Brainstem	D 0.03cc	15 Gy	20 Gy
SpinalCord_PRV05	D 0.03cc	15 Gy	20 Gy
Brainstem_PRV03	D 0.03cc	15 Gy	20 Gy
OpticNrv_L or OpticNrv_R	D 0.03cc	15 Gy	20 Gy
OpticChiasm	D 0.03cc	15 Gy	20 Gy
Mandible	D 0.03cc	20 Gy	108% D P_TV_High
Esophagus	D 0.03cc	20 Gy	108% D P_TV_High
Trachea	D 0.03cc	20 Gy	108% D P_TV_High
BrachialPlexus_L or BrachialPlexus_R	D 0.03cc	20 Gy	105% D P_TV_High

**Recommended**

*Dose Level 1 (42 Gy in 10 fractions)*

Structure	Dosimetric Parameter	Recommended Constraint
Mandible	V 20 Gy V 25 Gy	< 50% < 33%
Parotid_L or Parotid_R	D mean	18 Gy
GlnD_Submand_L or GlnD_Submand_R	D mean	27 Gy
Pharynx	D mean	30 Gy
LarynxGSL	D mean	30 Gy
Lips	D 0.03cc	20 Gy
Oral Cavity	D mean	20 Gy
Esophagus	D mean	20 Gy

*Dose Level 2 (39 Gy in 8 fractions)*

Structure	Dosimetric Parameter	Recommended Constraint
Mandible	V 20 Gy V 25 Gy	< 50% < 33%
Parotid_L or Parotid_R	D mean	17 Gy
GlnD_Submand_L or GlnD_Submand_R	D mean	25 Gy
Pharynx	D mean	29 Gy
LarynxGSL	D mean	29 Gy
Lips	D 0.03cc	19 Gy
Oral Cavity	D mean	19 Gy
Esophagus	D mean	19 Gy

### *Dose Level 3 (32.5 Gy in 5 fractions)*

Structure	Dosimetric Parameter	Recommended Constraint
Mandible	V 15 Gy V 20 Gy	< 50% < 33%
Parotid_L or Parotid_R	D mean	13 Gy
GlnD_Submand_L or GlnD_Submand_R	D mean	20 Gy
Pharynx	D mean	22 Gy
LarynxGSL	D mean	22 Gy
Lips	D 0.03cc	15 Gy
Oral Cavity	D mean	15 Gy
Esophagus	D mean	15 Gy

#### **5.1.5 Treatment Verification**

Daily CBCT is required for treatment setup

## **6 ADVERSE EVENTS: DEFINITIONS, COLLECTION, AND REPORTING REQUIREMENTS**

### **6.1 Definitions**

#### **6.1.1 Adverse Event (AE)**

An AE is defined as any untoward medical occurrence in a patient or clinical investigation subject administered a pharmaceutical product and which does not necessarily have to have a causal relationship with this treatment. (International Conference on Harmonisation [ICH], E2A, E6).

This includes the following:

- Adverse events not previously observed in the subject that emerge during the protocol-specified adverse event reporting period, including signs or symptoms associated with head and neck cancer that were not present prior to the adverse event reporting period.
- Complications that occur as a result of protocol-mandated interventions (e.g., invasive procedures such as cardiac catheterizations)
- If applicable, adverse events that occur prior to assignment of study treatment associated with medication washout, no treatment run-in, or other protocol-mandated intervention.
- Preexisting medical conditions (other than the condition being studied) judged by the investigator to have worsened in severity or frequency or changed in character during the protocol-specified adverse event reporting period.

This study will utilize the NCI Common Terminology Criteria for Adverse Events (CTCAE) version 5.0, located on the CTEP web site:

AEs may be spontaneously reported by the patient and/or in response to an open question from study personnel or revealed by observation, physical examination or other diagnostic procedures.

### 6.1.2 Serious Adverse Event (SAE)

Serious Adverse Event (SAE) means any untoward medical occurrence that results in any of the following outcomes:

- **Death.** Results in death.
- **Life threatening.** Is life threatening (refers to an AE in which the patient was at risk of death at the time of the event. It does not refer to an event which hypothetically might have caused death if it were more severe).
- **Hospitalization.** Requires inpatient hospitalization or prolongation of an existing hospitalization (see clarification in the paragraph below on planned hospitalizations).
- **Disability/incapacity.** Results in persistent or significant disability or incapacity. (Disability is defined as a substantial disruption of a person's ability to conduct normal life functions).
- **Pregnancy**
- **Congenital anomaly/birth defect:** Results in a congenital anomaly/birth defect in a neonate/infant born to a mother exposed to the IMP.
- **Medically important event.** This refers to an AE that may not result in death, be immediately life threatening, or require hospitalization, but may be considered serious when, based on appropriate medical judgment, may jeopardize the patient, require medical or surgical intervention to prevent one of the outcomes listed above, or involves suspected transmission via a medicinal product of an infectious agent. Examples of such medical events include allergic bronchospasm requiring intensive treatment in an emergency room or at home, blood dyscrasias or convulsions that do not result in inpatient hospitalization, or the development of drug dependency or drug abuse; any organism, virus, or infectious particle (e.g., prion protein transmitting Transmissible Spongiform Encephalopathy), pathogenic or nonpathogenic, is considered an infectious agent.

### 6.1.3 Assessment of Severity of Adverse Events

The adverse event severity grading scale for the NCI CTCAE v5.0 will be used for assessing adverse event severity. The below table should be used for assessing severity for adverse events that are not specifically listed in the NCI CTCAE.

#### Adverse Event Severity Grading Scale for Events Not Specifically Listed in NCI CTCAE

Grade	Severity
1	Mild; asymptomatic or mild symptoms; clinical or diagnostic observations only; or intervention not indicated

2	Moderate; minimal, local, or non-invasive intervention indicated; or limiting age-appropriate instrumental activities of daily living a
3	Severe or medically significant, but not immediately life-threatening; hospitalization or prolongation of hospitalization indicated; disabling; or limiting self-care activities of daily living b,c
4	Life-threatening consequences or urgent intervention indicated
5	Death related to adverse event

**Notes:**

a. Instrumental activities of daily living refer to preparing meals, shopping for groceries or clothes, using the telephone, managing money, etc.

b. Examples of self-care activities of daily living include bathing, dressing and undressing, feeding oneself, using the toilet, and taking medications, as performed by patients who are not bedridden.

c. If an event is assessed as a "significant medical event," it must be reported as a serious adverse event.

d. Grade 4 and 5 events must be reported as serious adverse events.

### 6.1.4 Attribution of an Adverse Event

All AEs and SAEs whether volunteered by the subject, discovered by study personnel during questioning, or detected through physical examination, laboratory test, or other means will be reported appropriately. Each reported AE or SAE will be described by its duration (i.e., start and end dates), regulatory seriousness criteria if applicable, suspected relationship to study intervention (see following guidance), and actions taken.

An assessment of the relationship between the adverse event and the medical intervention, using the following categories:

**Definitely Related:** *The AE is clearly related to the intervention.* There is clear evidence to suggest a causal relationship, and other possible contributing factors can be ruled out.

**Probably Related:** *The AE is likely related to the intervention.* There is evidence to suggest a causal relationship, and the influence of other factors is unlikely.

**Possibly Related:** *The AE may be related to the intervention.* There is some evidence to suggest a causal relationship (e.g., the event occurred within a reasonable time after administration of the trial intervention). However, the influence of other factors may have contributed to the event (e.g., the subject's clinical condition, other concomitant events).

**Unlikely:** *The AE is doubtfully related to the intervention.* A clinical event, including an abnormal laboratory test result, whose temporal relationship to drug administration makes a causal relationship improbable (e.g., the event did not occur within a reasonable time after administration of the trial intervention) and in which other drugs or chemicals or underlying disease provides plausible explanations (e.g., the subject's clinical condition, other concomitant treatments).

**Unrelated:** *The AE is clearly NOT related to the intervention.* The AE is completely independent of study intervention, and/or evidence exists that the event is definitely related to another etiology.

To ensure consistency of AE and SAE causality assessments, investigators should apply the following general guideline:

Yes: Related (definitely, probably, possibly, unlikely)

There is a plausible temporal relationship between the onset of the AE and administration of the radiotherapy and the AE cannot be readily explained by the subject's clinical state, intercurrent illness, or concomitant therapies; and/or the AE follows a known pattern of response to the study drug or with similar treatments; and/or the AE abates or resolves upon discontinuation of the radiation therapy or dose reduction and, if applicable, reappears upon re- challenge.

No: Not Related (unrelated)

Evidence exists that the AE has an etiology other than the radiation therapy (e.g., preexisting medical condition, underlying disease, intercurrent illness, or concomitant medication); and/or the AE has no plausible temporal relationship to radiotherapy administration (e.g., cancer diagnosed 2 days after first dose of study drug).

For patients receiving combination therapy, causality will be assessed individually for each protocol-mandated therapy.

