**Table 2**

Attribution	SAE				AE		
	Grade 1, 2 & 3		Grade 4 and 5		Grade 3	Grade 4	
	Expected	Unexpected	Expected	Unexpected	Unexpected	Expected	Unexpected
Unrelated Unlikely	IRB  and DSMC- Routine Review 	IRB  and DSMC- Routine Review 	IRB  - Routine Review 	IRB  - Routine Review 	DSMC  - Routine Review	DSMC  - Within 5 calendar days	DSMC  - Within 5 calendar days
Possible Probable Definite		IRB  and DSMC  - Within 5 calendar days	DSMC  - Within 5 calendar days	IRB  and DSMC  - Within 5 calendar days			

Guidance on Adverse Event Reporting to the IRB is available online at [MCW IRB Policies and Procedures](#).

For routine reporting, the events will be reported to IRB as part of the annual continuing progress report, and the DSMC will review events entered in OnCore® at the time of scheduled monitoring.

For expedited DSMC reporting, study coordinator/research nurse must notify the DSMC via email. For AEs, include the subject ID, date of event, grade, relatedness, expectedness, and a short narrative. For SAEs, DSMC will review the SAE report entered into OnCore®.

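### The Yes/No causality guideline in section 6.1.4 counts *Unlikely* events as related to radiotherapy, against the section's own definition and Table 2

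*Combined protocol and SAP*

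**What the plan says.** Section 6.1.4 of the combined protocol and SAP asks for each adverse event to be rated on five levels: definitely, probably, possibly, unlikely or unrelated. The headline definition of *Unlikely* is "The AE is doubtfully related to the intervention". Its fuller text describes an event "whose temporal relationship to drug administration makes a causal relationship improbable" and for which other drugs, chemicals or the underlying disease offer a plausible explanation.

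The section then gives a general guideline, intended to make causality assessments consistent, that reduces the five levels to two:

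- Yes group: "Yes: Related (definitely, probably, possibly, unlikely". Its first criterion is "There is a plausible temporal relationship between the onset of the AE and administration of the radiotherapy", together with the absence of a ready explanation in the patient's condition, intercurrent illness or other treatment. Further alternatives are joined by and/or: a response pattern already known for this or similar treatment, or improvement when treatment is stopped or reduced.
- No group: "No: Not Related (unrelated". Its criteria are evidence of another etiology, and/or that "the AE has no plausible temporal relationship to radiotherapy administration".

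Table 2 in section 6.2.3 sets reporting routes in two attribution rows, labelled "Unrelated Unlikely" and "Possible Probable Definite".

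**The concern.** A guideline meant to produce consistent coding sends one whole category to the side that its definition argues against. Two investigators could code the same *Unlikely* event differently and each cite the protocol: one the Yes list, the other the definition, the No criteria or the grouping in Table 2.

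Safety is the main product of this 18-patient Phase I trial. Any listing or table split into related and not related would, if built on the guideline, count events that the investigator thought improbable as radiation effects. Section 6.2.1 also uses relatedness twice without naming a level: for the follow-up of adverse events until they resolve, and for the SAEs to be reported after the 12-month period. A reader looking for the meaning of related or attributed in those rules would naturally turn to the Yes/No guideline.

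**Working it through.** The plan states no figure on this point and no arithmetic decides it. The check sets the texts side by side.

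**1. Definition of *Unlikely* against the Yes and No criteria (section 6.1.4)**

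| Element | *Unlikely* as defined | Yes criteria | No criteria |
|---|---|---|---|
| Timing | Makes causality improbable | Plausible | Not plausible |
| Other explanation | Plausible one exists | None readily available | Another etiology is evident |
| Other routes | None given | Known response pattern, or improvement on stopping or reducing treatment | None given |

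An event that meets the definition fails both parts of the first Yes criterion and lies close to both No criteria. The match with No is not exact, because No speaks of evidence for another etiology and *Unlikely* only of a plausible one. The conflict with Yes is not total either, because an *Unlikely* event could occasionally satisfy one of the and/or alternatives. That would justify a Yes for the single event, but not for the category.

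**2. The guideline against Table 2 (section 6.2.3)**

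The guideline splits the scale between unlikely and unrelated. Table 2 splits it between possible and unlikely. The document does not say which split governs a related/not-related summary.

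**3. Table 2, cell by cell**

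The table has seven columns, four for SAEs and three for AEs. The two attribution rows carry different entries in three of them: unexpected Grade 1–3 SAE, expected Grade 4–5 SAE and unexpected Grade 4–5 SAE. In each of these the row containing *Unlikely* gives routine review and the other row gives 5 calendar days. In the remaining four columns the second row appears blank in the text available, possibly because cells were merged. *Unlikely* is named in the first row and no row is labelled related, so an *Unlikely* SAE has one timing: routine review.

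**4. Where the Yes/No code could enter**

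- DLT definition (section 7.2.1): toxicity and death count only if probably or definitely related. The third route, failure to complete radiotherapy within 30 days, excludes disease progression and unrelated death without referring to the guideline.
- TITE-CRM and the 33% target (section 7.1) and the accrual suspension rule (section 7.4, read as concerning the 12-month DLT rate) work through that DLT definition.
- Secondary toxicity analysis (section 7.2.2): CTCAE scores over time, described without an attribution filter.
- Deaths in the reporting period (section 6.2.2.2): reported whatever the attribution.
- Section 6.2.1: follow-up of events related to treatment, and SAEs after month 12 attributed to treatment. Neither names a level, so the code could enter here.
- Any summary of treatment-related events: section 7 plans none explicitly, but the code would enter one if it were produced.

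**The case against.** The strongest reply is that nothing important turns on the slip. The five-level rating is kept, so no information is lost. The error runs towards over-inclusion, which some would accept as caution in a safety study. Section 7 plans no related/not-related table. Section 6.2.1 first says that adverse events are followed to resolution without any condition on relatedness, so extra follow-up is doubtful, and its rule for SAEs after month 12 does not cite the Yes/No code.

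Most of this stands, and it is why the point is minor. It does not remove the contradiction. The document nowhere says that the wide Yes group is deliberate caution, and both the Yes criteria and Table 2 speak against that reading. The rule for SAEs after month 12 remains open to either interpretation.

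Three stronger readings are tempting but not supported:

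- **The same SAE has two reporting deadlines.** A reader might infer this by carrying the Yes code into the lower row of Table 2. Nothing instructs that step, and Table 2 names *Unlikely* directly. It is a possible misreading, not a second rule.
- **Deaths from recurrent cancer would be coded as radiation deaths.** The definition of *Unrelated*, the No criteria and section 7.2.1 all steer such deaths to *Unrelated*, where there is no conflict.
- **A share of the expected deaths would be misattributed.** The document gives no proportion of deaths or events rated *Unlikely*, so any such count would be a guess.

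**Conclusion.** The inconsistency is real and minor. The Yes list contradicts the definition of *Unlikely*, largely contradicts the Yes and No criteria, and conflicts with the grouping in Table 2. The exposure is limited to related/not-related summaries, if they are built on the guideline, and to the two rules in section 6.2.1 that leave the level of relatedness open. Dose assignment, DLT counts, the stopping rule and the Table 2 deadlines are unaffected, provided that they are applied from the five-level rating as written.

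The number of events involved cannot be estimated from the documents. For scale only, one patient wrongly counted in a summary over all 18 moves a proportion by 1/18 = 5.6 percentage points.

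**What to change.** Reconcile section 6.1.4 with its own definitions and with Table 2. List definitely, probably and possibly under Yes, and unlikely and unrelated under No. Add a sentence saying that this split governs every related/not-related summary and the two relatedness-dependent rules in section 6.2.1, while Table 2 and the DLT definition continue to use the five-level rating.

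The cost is one word moved and one sentence added. Any events already coded Yes on the strength of an *Unlikely* rating need recoding, which can be done from the five-level rating already recorded. No patients, visits or design features change.

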### **6.1.5 Expectedness of an Adverse Event**

Study Investigator or treating Physician will be responsible for determining whether an AE is expected or unexpected as indicated in the protocol, informed consent form and/or drug information brochure. Expected adverse events of study intervention are those adverse events that are listed or characterized in the Package Insert (P.I) or current Investigator Brochure (I.B), when applicable.

Unexpected adverse events of study intervention are those not listed in the P.I or current I.B or not identified that are not attributable to radiotherapy. This includes adverse events for which the specificity or severity is not consistent with the description in the P.I. or I.B. For example, under this definition, hepatic necrosis would be unexpected if the P.I. or I.B. only referred to elevated hepatic enzymes or hepatitis. An AE will be considered unexpected if the nature, severity, or frequency of the event is NOT consistent with the risk information previously described for the study intervention (radiotherapy).

